NCT Number: NCT02536963

Study Title: Improving Quality Vision Outcomes in Managed Care Setting While Reducing Cost by Use of Accurate, Automated Screening

Document: Study Protocol

Date Created: August 2015

Objectives and Purpose

2.1 The purpose of this study is to assess the performance of the Pediatric Vision Scanner at identifying amblyopia/strabismus on children older or equal to 2 years of age, and less than 6 years of age in a busy pediatric clinic setting and to compare it to an examination comprised of visual acuity testing, stereopsis, eye alignment, and cycloplegic refraction.

2.2 The hypothesis is that the false positive rate of REBIScan is 10% or less. The proportion of patients without amblyopia or strabismus will be less than 10% of patients screened positive by the device.

- Amblyopia will be defined as a two or more line difference between the eyes or a clear fixation preference in either eye, in the presence of a known amblyogenic factor.
 - 2-3 year old: vision >20/50
 - 4 year old - vision > 20/40
 - 5 year old - vision > 20/30
- Strabismus is defined as misalignment of the eyes.

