12.0 Statistical considerations

This study is the second of a two-phased study. The first phase was a pilot and feasibility study to understand the utility of using the PVS device within Kaiser Permanente. This second phase is to determine the sensitivity and specificity of the device and its feasibility for widespread deployment in a primary care setting.

The collected data will generate patient demographic and clinical descriptives to describe the study population.

The outputs that will be calculated are sensitivity and specificity for detecting amblyopia or strabismus. The current published data on PVS sensitivity and specificity is 97% and 87% respectively. Error! Bookmark not defined. It is anticipated that sensitivity will be within 5% of the published results; that is, 92% sensitivity and 82% specificity (contained within the calculated 95% confidence intervals.) Assuming a 5% prevalence rate of the conditions, in a sample size of 300 children we anticipate 15-20 children presenting with amblyopia or strabismus; therefore we expect to identify 14-18 cases, while having no more than 45 false referrals.

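### The 10% limit on the false positive rate in Section 2.2 is inconsistent with the specificity of 82% to 87% on which Section 12 plans the study

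*Protocol*

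**What the plan says.** Section 2.2 (Objectives and Purpose) contains the protocol's only stated hypothesis: "The hypothesis is that the false positive rate of REBIScan is 10% or less". The next sentence puts the limit in different terms: "The proportion of patients without amblyopia or strabismus will be less than 10% of patients screened positive by the device". That is a share of screen positives (1 - positive predictive value), not of unaffected children.

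Section 12.0 (Statistical considerations) names sensitivity and specificity as the outputs and gives these planning figures:

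- Prior performance: "The current published data on PVS sensitivity and specificity is 97% and 87% respectively".
- What is anticipated in this study, as a tolerance of 5 percentage points: "that is, 92% sensitivity and 82% specificity".
- Numbers of children: "Assuming a 5% prevalence rate of the conditions, in a sample size of 300 children we anticipate 15-20 children presenting with amblyopia or strabismus".
- Expected yield: "therefore we expect to identify 14-18 cases, while having no more than 45 false referrals".

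Neither section refers to the other's figures, and neither gives a test or decision rule for the 10% limit.

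**The concern.** A false positive rate of 10% or less, in the usual sense, is the same statement as a specificity of 90% or more. Section 12 does not plan for 90%. It starts from 87% and allows for 82%. So the hypothesis sets a limit that the protocol's own planning values do not reach.

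False positives are the subject of the only hypothesis, and specificity is one of the two outputs to be calculated. If the device performs as published, the result will agree with what Section 12 expects and will most likely lie above the limit in Section 2.2. The report would then have two yardsticks for the same quantity, with nothing in the protocol to say which one governs the conclusion.

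**Working it through.** **Inputs, all from the protocol.** N = 300; prevalence 5%; 15 to 20 cases; specificity 87% (published) and 82% (anticipated); sensitivity 92% (anticipated); at most 45 false referrals (all Section 12). Limit of 10% (Section 2.2).

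**Step 1. Reproduce Section 12's own counts.**

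- Cases = 300 × 0.05 = 15. The upper figure of 20 corresponds to 20/300 = 6.7%.
- Detected cases = cases × sensitivity: 15 × 0.92 = 13.8 and 20 × 0.92 = 18.4, which gives the stated 14 to 18.
- Unaffected children = 300 - 15 = 285, or 300 - 20 = 280.
- The 45 does not follow from either stated specificity (Step 2). It equals 15% of all 300 children, and as a share of the unaffected it corresponds to a specificity of about 84%. As an upper bound it is compatible with 87% but lies below the count expected at 82%.

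**Step 2. Put both sections on one scale.** False referrals = unaffected × (1 - specificity).

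| Source | 1 - specificity | Of 285 | Of 280 |
|---|---|---|---|
| Section 2.2 limit, 10% | 10% | 28.5, so at most 28 | 28 |
| Section 12, published 87% | 13% | 37.1 | 36.4 |
| Section 12, anticipated 82% | 18% | 51.3 | 50.4 |
| Section 12, ceiling of 45 | 15.8% to 16.1% | 45 | 45 |

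Both planning specificities give a rate above 10%. The ceiling permits a rate above 10% but does not require one.

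**Step 3. Chance of an observed rate at or below 10%.** This is the exact binomial probability P(X ≤ 28), with X the number of false referrals among n unaffected children.

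| True specificity | n = 285 | n = 280 |
|---|---|---|
| 87% | 0.062 | 0.077 |
| 82% | 0.00009 | 0.00014 |
| 90% | 0.51 | 0.55 |

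The last row is for reference: even a device exactly at the limit would show 10% or less only about half the time.

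**Step 4. The reading that Section 2.2 spells out.** With 45 false referrals and 14 to 18 detected cases, the false share of screen positives is 45/(45 + 14) = 76% or 45/(45 + 18) = 71%. A share of 10% corresponds to detected cases/9 false referrals, that is 14/9 = 1.6 to 18/9 = 2.0 children. The gap is far wider on this reading, so 1 - specificity is the lenient one.

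**The case against.** Several counter-arguments deserve weight.

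- *The protocol does not define the rate as 1 - specificity.* Correct. The second sentence of Section 2.2 uses screen positives as the denominator, which is a defect in its own right. It does not remove the conflict, because Step 4 shows that the conflict is larger on that reading. Correcting the denominator alone would still leave 10% against 13% to 18%.
- *A hypothesis may be more ambitious than earlier data.* It may, but Section 12 also says what is anticipated in this study, and the value it spells out, 82%, is further from 90% than the published figure. A two-sided reading of the 5-point tolerance would reach 92% specificity (8% false positives), but the text does not state that.
- *Section 12 sets no success criterion, and 45 is a ceiling.* This stands. The section speaks of what is anticipated and expected. A count of 28 or fewer would satisfy the 45 and the 10% together.

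For that last reason, two stronger inferences are not supported. A reader might conclude that the study is planned to fail its hypothesis, or that most studies of a device at 87% would pass under Section 12 and fail under Section 2.2. Both treat the expectation of 45 as a pass mark, which the protocol never does. A reader might also infer that the sponsor could pick the favourable yardstick afterwards. The protocol gives the statistical analysis to the health system's biostatisticians (end of Section 10), and a separate analysis plan may fix the rule. No such intent can be read from the text.

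**Conclusion.** The point holds as an inconsistency between a hypothesised limit and the planning values for the same quantity. The limit allows 28 false referrals, against 36 to 37 expected at 87% specificity and 50 to 51 at 82%. The chance of an observed rate at or below 10% is about 6% to 8% if 87% is true and about 0.01% if 82% is true.

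These figures assume 280 to 285 unaffected children, independent results between children, and a comparison of the observed rate with 10%. The last is an assumption made for the calculation, since the protocol states no rule. Failure is unlikely to be avoided at the planning values, but it is not certain: at 37 of 285 the exact 95% interval is 9.3% to 17.4% and still contains 10%.

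A separate analysis plan could add a decision rule, but it could not make the two protocol statements agree. Because the limit belongs to the only hypothesis and is cheap to correct, it should be corrected before analysis.

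**What to change.** In Section 2.2, define the false positive rate as 1 - specificity among children without amblyopia or strabismus, and delete or replace the sentence on the share of screen positives. If that sentence stays, it still demands fewer than 10% false results among positives, whatever else is changed. Then use one specificity target, with its matching count, in both sections:

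- **(a)** Set the limit in Section 2.2 to the complement of the Section 12 planning specificity and make the false-referral figure agree: 18% and about 51 for 82%, or 13% and about 37 for 87%. The 45 must change too. An 18% limit beside a ceiling of 45 would create a new contradiction.
- **(b)** Keep 10%, restate the Section 12 target as a specificity of at least 90% with at most 28 false referrals, and say openly that the published 87% falls short of it, with under a 10% chance of an observed rate at or below 10% if 87% is true.

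The cost is wording in two sections. No new data are needed, and the sample of 300 and the examinations are unchanged. The price is a less ambitious target under (a) or a less favourable stated chance of meeting it under (b).

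### The protocol's only stated hypothesis limits false positives and sets no limit on sensitivity, so confirming it would not answer the question in Section 2.1

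*Protocol*

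**What the plan says.** Protocol Section 2.1 gives the purpose: to "assess the performance of the Pediatric Vision Scanner at identifying amblyopia/strabismus" in young children in a pediatric clinic, compared with an eye examination.

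Section 2.2 states the hypothesis in two sentences. The first is "The hypothesis is that the false positive rate of REBIScan is 10% or less". The second is "The proportion of patients without amblyopia or strabismus will be less than 10% of patients screened positive by the device". Read literally, the first limits false positives among unaffected children (1 - specificity), and the second limits false positives among screen-positive children (1 - positive predictive value).

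Section 12.0 states the aim of the phase: "This second phase is to determine the sensitivity and specificity of the device and its feasibility for widespread deployment in a primary care setting". It adds: "The outputs that will be calculated are sensitivity and specificity for detecting amblyopia or strabismus". It cites earlier results ("The current published data on PVS sensitivity and specificity is 97% and 87% respectively") and gives the values anticipated here: "that is, 92% sensitivity and 82% specificity (contained within the calculated 95% confidence intervals". With 5% prevalence and 300 children it anticipates 15-20 cases, 14-18 of them identified, and at most 45 false referrals. These are worded as expectations.

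The only other acceptance criterion is at the end of Section 10.0. It concerns test time and number of attempts, not accuracy.

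**The concern.** In a screening study the main failure is an affected child whom the device passes. Sections 2.1 and 12.0 treat detection as the question, but the hypothesis in Section 2.2 covers only the false-positive side. If the study is summarised by whether its hypothesis was confirmed, a positive answer would be compatible with almost any sensitivity. A reader could then take a confirmed hypothesis as evidence that the device finds affected children, which Section 2.2 does not test.

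**Working it through.** **Inputs.** From Section 12.0: N = 300; prevalence 5%; 15-20 cases, hence 285-280 non-cases; anticipated sensitivity 92% and specificity 82%; published 97% and 87%; 14-18 cases identified; at most 45 false referrals. From Section 2.2: 10% as the limit in both sentences.

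**Notation.** TP = affected children referred; FP = unaffected children referred. Sensitivity = TP / cases. Sentence 1 limits FP / non-cases. Sentence 2 limits FP / (TP + FP).

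**1. The plan's own figures.** 300 × 0.05 = 15 cases. 15 × 0.92 = 13.8 and 20 × 0.92 = 18.4, so 14-18 identified is reproduced. The 45 false referrals do not follow from 82% specificity (285 × 0.18 = 51.3; 280 × 0.18 = 50.4) or from 87% (285 × 0.13 = 37.1; 280 × 0.13 = 36.4). 45 is 15% of all 300 children.

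**2. Can the hypothesis be met without useful detection?** The table assumes 15 cases and 285 non-cases.

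| Device | Sensitivity | Sentence 1 | Sentence 2 |
|---|---|---|---|
| Passes every child | 0/15 = 0% | 0/285 = 0%, met | 0/0, undefined |
| Refers one true case, nobody else | 1/15 = 6.7% | 0/285 = 0%, met | 0/1 = 0%, met |
| Refers 5% of children at random | 5% on average | met with P = 0.9997 | met with P of about 2 in 10 million |

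For the random device, sentence 1 is met if FP ≤ 28. With FP ~ Binomial(285, 0.05), P(FP ≤ 28) = 0.9997; with 280 non-cases it is 0.9998. For sentence 2, the joint binomial probability that FP / (TP + FP) < 0.10 with at least one referral is 2 × 10⁻⁷ (15 cases) to 4 × 10⁻⁷ (20 cases). At 2% random referral it is about 0.001.

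The second row is decisive: both sentences hold at about 7% sensitivity.

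**3. The 10% limit against Section 12.0.**
- Sentence 1: specificity of 87% or 82% means a false positive rate of 13% or 18%. 45 false referrals give 45/285 = 15.8% or 45/280 = 16.1%. The chance of observing FP ≤ 28 is 6-8% at 87% specificity and about 0.01% at 82%.
- Sentence 2: 45/(14 + 45) = 76% and 45/(18 + 45) = 71% non-cases among positives. To stay below 10% with 14-18 true positives, only one false positive is allowed: 1/15 = 6.7% but 2/16 = 12.5%; 1/19 = 5.3% but 2/20 = 10.0%, which is not below 10%. That needs a specificity of 284/285 or 279/280, both 99.6%.

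**4. What a sensitivity condition could do with 15-20 cases.** As an illustration, require the exact (Clopper-Pearson) 95% lower limit to exceed 50%. This needs 12/15 detected (lower limit 51.9%) or 15/20 (50.9%). At a true sensitivity of 92% the condition is met with probability 0.973 or 0.996. For random referral at 10% or less, the probability is below 10⁻⁹. Precision is limited: 14/15 gives an interval of 68% to 99.8%, and 18/20 gives 68% to 98.8%.

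**The case against.** The strongest reply is that sensitivity is already in the plan. Section 12.0 makes it an output, anticipates 92% and expects 14-18 of 15-20 cases to be found, so a device that missed most cases would be exposed in the results. Nothing makes Section 2.2 a pass/fail rule, and a formal threshold could sit in a statistical analysis plan that is not shown. This stands to a large extent: missed cases are not absent from the plan, and the damage is confined to what a confirmed hypothesis can be taken to mean. It does not remove the point, because the protocol itself states the hypothesis and leaves detection out of it.

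A reader might infer that a device referring a few children at random would confirm Section 2.2. The text does not support that. Such a device meets sentence 1 but almost surely fails sentence 2, because about 95% of its positives would be non-cases.

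A reader might also infer that the hypothesis rewards lower sensitivity throughout. Under sentence 2 it does not, because missed cases shrink the denominator. With 14 true and 1 false positive the share is 1/15 = 6.7%; if six more cases are missed it becomes 1/9 = 11.1% and the limit is exceeded. Sentence 2 therefore responds to missed cases but puts no floor under sensitivity.

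Finally, the extreme devices are hypothetical. Section 4.1 fixes the referral cut-off, and the cited accuracy is high. The examples show what the hypothesis leaves open and do not predict how this device will behave.

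**Conclusion.** The point holds in a limited form. Neither sentence of Section 2.2 bounds sensitivity. A pass-all device meets sentence 1, and a device that refers a single true case meets both at 6.7% sensitivity (5% with 20 cases). Confirming Section 2.2 alone therefore does not answer Section 2.1. It does not follow that the study ignores missed cases, or that an uninformative random referrer would pass the whole of Section 2.2.

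On the plan's own figures the nearer difficulty is the opposite one: at specificities of 82-87% the device would most likely fail Section 2.2 on either measure, however well it detects cases. Any rewrite has to deal with both.

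The figures assume 300 analysed children with 15-20 cases, independent results between children, and the literal reading of the two sentences as different measures. This is an inexpensive improvement; the planned sensitivity and specificity estimates remain valid without it.

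**What to change.** Restate Section 2.2 as a joint hypothesis that is confirmed only if both parts hold:

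1. **False positives.** Choose one definition. The natural one is the rate among unaffected children, which matches the specificity in Section 12.0. Reconcile the 10% limit with the 82-87% specificity and the 45 false referrals given there. If the share among screen-positives is dropped, say so.
2. **Sensitivity.** Add a limit that the sponsor sets in advance and ties to the 92% in Section 12.0. The 50% lower limit in the working is only an illustration chosen to be attainable. It would accept 12/15 (80%) or 15/20 (75%) detected, and the sponsor may want a stricter limit.

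State that meeting the false-positive part alone does not support a conclusion about detection.

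The change is to wording. It needs no extra patients, procedures or data, since Section 12.0 already calculates both measures. The sponsor must commit to a sensitivity limit and accept that 15-20 cases give a wide interval. With the illustrative limit, the sensitivity part would fail by chance in at most 2.7% of studies at 92% sensitivity (1 - 0.973). If the 10% limit is left unreconciled, the false-positive part would usually fail on its own.

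### Section 2.2 states its 10% hypothesis as two different quantities; on Section 12's own figures the second would be 65-79%, not under 10%

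*Protocol*

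**What the plan says.** Section 2.2 of the protocol gives the study's only stated hypothesis in two consecutive sentences. The first reads "The hypothesis is that the false positive rate of REBIScan is 10% or less". The second reads "The proportion of patients without amblyopia or strabismus will be less than 10% of patients screened positive by the device".

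Section 12.0 supplies the planning figures:

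- Published accuracy: "The current published data on PVS sensitivity and specificity is 97% and 87% respectively".
- Lower anticipated values, five points below: "that is, 92% sensitivity and 82% specificity".
- Case numbers: "Assuming a 5% prevalence rate of the conditions, in a sample size of 300 children we anticipate 15-20 children presenting with amblyopia or strabismus".
- Yield: "therefore we expect to identify 14-18 cases, while having no more than 45 false referrals".

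Section 12.0 names sensitivity and specificity as the outputs to be calculated. It does not mention predictive values.

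**The concern.** False positive rate normally means false positives divided by all children without the condition. The second sentence of Section 2.2 instead puts the screen-positives in the denominator. When about 5% of children are affected, the two proportions are far apart, because a small fraction of a large unaffected group easily outnumbers the true cases. A reader cannot tell which quantity the 10% limit governs, and the same data could be reported as meeting one sentence and missing the other.

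The limit also has to fit Section 12. If the device performs exactly as published, that is the expected result there. It would nevertheless miss the second sentence almost surely, and the first sentence most of the time. In addition, the ceiling on false referrals should follow from a stated specificity, and it appears not to.

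**Working it through.** **Inputs, all from Section 12.0.** N = 300. Affected children D = 15 (5% of 300) or 20 (6.7%). Unaffected children H = 300 - D = 285 or 280. Sensitivity/specificity (se/sp) = 97%/87% or 92%/82%.

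**Formulas.** True positives TP = D × se. False positives FP = H × (1 - sp). False positive rate = FP/H = 1 - sp. False share of positives = FP/(TP + FP) = 1 - PPV.

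**1. The plan's own yield.**

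- Cases found at 92% sensitivity: 15 × 0.92 = 13.8 and 20 × 0.92 = 18.4. This reproduces the stated 14-18.
- False referrals at the paired 82% specificity: 285 × 0.18 = 51.3 and 280 × 0.18 = 50.4.
- False referrals at 87%: 285 × 0.13 = 37.05 and 280 × 0.13 = 36.4.
- The stated 45 matches neither. It implies specificity of 1 - 45/285 = 84.2% or 1 - 45/280 = 83.9%.
- Exact binomial chance of more than 45 false referrals (D = 15 / D = 20): 81% / 77% at 82% specificity, 7% / 6% at 87%.

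**2. The second sentence, expected false share of positives.**

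| D | se/sp | TP | FP | FP/(TP + FP) |
|---|---|---|---|---|
| 15 | 97%/87% | 14.55 | 37.05 | 37.05/51.60 = 71.8% |
| 15 | 92%/82% | 13.8 | 51.3 | 51.3/65.1 = 78.8% |
| 20 | 97%/87% | 19.4 | 36.4 | 36.4/55.8 = 65.2% |
| 20 | 92%/82% | 18.4 | 50.4 | 50.4/68.8 = 73.3% |

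Section 12's own counts give 45/(45 + 18) = 71.4% and 45/(45 + 14) = 76.3%.

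A specificity of 92%, five points above the published value, still leaves 61.0-62.3% (D = 15) or 53.6-54.9% (D = 20) for sensitivity of 97% to 92%.

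**3. What the second sentence would require.** FP/(TP + FP) < 0.10 means FP < TP/9.

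- D = 15: FP below 13.8/9 = 1.53 to 14.55/9 = 1.62, so specificity of about 99.43-99.46%.
- D = 20: FP below 18.4/9 = 2.04 to 19.4/9 = 2.16, so specificity of about 99.23-99.27%.
- In whole children with 15 cases, at most 1 false positive: with all 15 found, 1/16 = 6.3% passes and 2/17 = 11.8% does not.
- In whole children with 20 cases, 2 are allowed if at least 19 are found (2/21 = 9.5%). Only 1 is allowed if 18 are found, since 2/20 is exactly 10%.
- Exact binomial chance of an observed share under 10%: below 10⁻¹³ at 97%/87%. Even at 97%/92% it is 1.2 × 10⁻⁹ (D = 15) and 2.1 × 10⁻⁸ (D = 20).

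**4. The two sentences are not equivalent.** Set the false positive rate at exactly 10%, which meets the first sentence, with sensitivity 97% to 92%. For D = 15, FP = 28.5 and the false share is 66.2-67.4%. For D = 20, FP = 28 and it is 59.1-60.3%.

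**5. The first sentence against Section 12.** Specificity of 87% and 82% gives false positive rates of 13% and 18%. An observed rate of 10% or less allows at most 28 false positives (28.5 or 28.0, rounded down). The binomial chance of that (H = 285 / H = 280) is:

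| True specificity | P(FP ≤ 28) |
|---|---|
| 87% | 6.2% / 7.7% |
| 90% | 51% / 55% |
| 92% | 89% / 91% |

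**The case against.** Five things can be said for the plan.

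- The protocol attaches no test, significance level or action to the 10% figure. Both quantities come from the same two-by-two table, so enrolment and data collection do not depend on which is meant. The one explicit acceptance criterion, on feasibility in Section 10.0, is untouched. This is right: the damage is to the meaning of the hypothesis and to how results are judged against it, not to the conduct of the study. But it is the only hypothesis stated.
- The second sentence may be the protocol's own definition of false positive rate, so that there is one quantity under a loose name. That removes the contradiction between the sentences, but it leaves the hypothesis resting on a target that Section 12's figures miss by more than 50 percentage points.
- The second target is not mathematically impossible. It could be met at specificity of about 99.2-99.5%. This stands, and the conclusion is conditional on Section 12's assumptions.
- A hypothesis may ask for more than published performance, so the first sentence is not an error in itself, and the 6-8% chance assumes true specificity of exactly 87%. This also stands. What is missing is any statement that the stricter limit is deliberate.
- The 45 lies between the counts implied by the two stated specificities and would rarely be exceeded at 87%. It fails only as a ceiling at 82%, a value Section 12 explicitly anticipates. The point is secondary, and the main conclusion does not rest on it.

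**Conclusion.** The concern holds. Section 2.2 applies one 10% limit to two non-equivalent quantities. Under Section 12's assumptions (300 children, 15-20 affected, accuracy between 97%/87% and 92%/82%), the quantity in the second sentence is expected to be 65-79%, and meeting the limit is practically ruled out. The quantity in the first sentence is expected to be 13-18%. A device performing exactly as published would miss the first limit about 92-94% of the time. Neither reading of the hypothesis therefore agrees with the planning figures, though the first could be kept as a deliberately demanding target. The probabilities treat children as independent with common sensitivity and specificity; the expected shares need no such assumption. This must be corrected because it concerns the study's sole stated hypothesis.

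**What to change.** In Section 2.2, state one measure and its denominator. The choice that fits the outputs named in Section 12.0 is the false positive rate, defined as false positives divided by children without amblyopia or strabismus (1 - specificity). Remove or correct the sentence that uses screen-positives as the denominator. Then either bring the 10% limit into line with the specificity assumed in Section 12.0, or say that it intentionally asks for more than the published 87%. The limit itself is the sponsor's choice.

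In Section 12.0, replace 45 with counts derived from the stated specificity: about 36-37 false referrals at 87% and about 50-51 at 82%. If the false share of positives is kept as a descriptive result, give its expected value of about 65-79%.

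The cost is protocol wording only, with no extra children, visits or procedures. The stated figures will look less favourable, and the sponsor must choose and justify one limit.
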